## 7.2 Sample Size and Accrual

The study will enroll 30 eligible patients that are being treated at UNC Hospitals. To test for a difference in change scores between response groups at a given time point (for example, mid-treatment change from pre-treatment) we will utilize the non-parametric Wilcoxon Rank Sum test. An advantage of using this nonparametric method is that the effect size is expressed in probabilistic terms, since the difference scores have been transformed into ranks, the statistical comparisons take place in this space, and the magnitude and variability of the difference scores are not needed. This means the power and sample size for each time point's difference scores will be the same.

Let  $X = x_1, x_2, \dots, x_n$  represent a sample of size  $n$  difference scores for responders and  $Y = y_1, y_2, \dots, y_n$  represent a sample of size  $n$  difference scores non-responders. Now let  $p = P(X > Y)$ , or the probability that a difference score in the responder group greater than the difference score in the non-responder group. Please note that we could just as easily frame the probability  $p = P(Y > X)$ . Intuitively, one can see that a  $p=0.5$  would mean that either  $X > Y$  and  $Y > X$  would be equally likely. This  $p$  would be the measure of the nonparametric or distribution-free effect size. The Wilcoxon signed-rank method tests the null hypothesis that the distributions of the two samples are equal, which corresponds to a  $p=0.5$ .

Assuming 30 patients complete the study, we will have approximately 90% power assuming  $p = 0.82$ , with a Type I error rate of 0.05 and utilizing the Wilcoxon Rank Sum test [1] to test for a difference in PET mean SUV from pre-treatment to mid-treatment. For correlating the fractional change in PET mean SUV with change in MRI tumor volume between time points, with  $n = 30$  subjects, we will have approximately 82.5% power to detect a Pearson correlation of at least 0.5, assuming a two-sided Type I error rate of 0.05 and utilizing the correlation test.

[1] Noether, G. E. (1987). Sample size determination for some common nonparametric tests. *Journal of the American Statistical Association*, 82(398), 645-647.

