## 7.3 Data Analysis Plans

Quantitative imaging measures (mean SUV, maximum SUV, MRI-based tumor

volume) will be compounded for all patients. Difference scores including the fractional change from pre-treatment to mid-treatment (early response) and the fractional change from pre-treatment to post-treatment (late response) will be computed for all quantities. Subjects will be classified into responders and non-responders on the basis of degree of necrosis (>90% necrosis = good response; <90% necrosis = poor response). Median, range, mean, and variance of each image measure will be computed for each response group. Differences in all quantitative measures between the response groups will be assessed with the non-parametric Wilcoxon Rank Sum test, and correlations between quantitative measures will be determined using the non-parametric Spearman's rank correlation coefficient and Pearson product-moment correlation coefficient. To develop a predictive model for early response, we will train a logistic regression classifier on the binary response data utilizing various PET SUV and MRI-based imaging measures (in terms of change from pre-treatment to mid-treatment) as covariates. All subsets selection with BIC will be used to determine the best combination of PET and MRI imaging measures to predict binary response, and empirical measures of predictive performance such as leave-one-out cross validation and Receiver-Operating-Characteristic (ROC) curves (evaluated as to the area under the ROC curve) will be computed.

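### The exploratory response model in 7.3 is fitted over all subsets in 30 patients with no bias-reduced fit, so its coefficients will tend to be too large, and separation is possible with no rule for it

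*Combined protocol and SAP*

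**What the plan says.** Section 7.2 fixes the size: "The study will enroll 30 eligible patients". Its power statement makes no allowance for dropout ("Assuming 30 patients complete the study, we will have approximately 90% power assuming" P(X>Y) = 0.82) and writes both response groups with the same n, which implies 15 and 15.

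Section 7.3 classifies response by necrosis (">90% necrosis = good response; <90% necrosis = poor response") and does not say how many responders are expected. It opens by naming three imaging quantities: mean SUV, maximum SUV and MRI tumor volume. For the prediction model, "we will train a logistic regression classifier on the binary response data utilizing various PET SUV and MRI-based imaging measures", taken as change from pre-treatment to mid-treatment. Then "All subsets selection with BIC will be used to determine the best combination of PET and MRI imaging measures to predict binary response". Performance is to be described by measures such as leave-one-out cross-validation and the area under the ROC curve.

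No penalised or bias-reduced fit is named, nor a limit on model size, nor a rule for separation or non-convergence. BIC is computed from a maximised likelihood, so ordinary maximum likelihood is the natural reading, although the text does not say so. Sections 2.3 and 7.1 class the model as exploratory.

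**The concern.** Ordinary logistic regression in a small sample gives coefficients that are too large on average, and choosing the best of several subsets adds to this. If some combination of markers divides responders from non-responders without error (complete separation), the maximum-likelihood estimate does not exist: odds ratios diverge and fitted probabilities go to 0 or 1. BIC gives no protection, because a separated model has zero deviance and so looks excellent.

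Section 1.1 says that the results may be used to plan later studies of mid-treatment prediction. Inflated or divergent coefficients would be a poor basis for that. With no rule in place, the analyst would have to choose a repair after seeing the outcomes.

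**Working it through.** **Inputs from the protocol.** 30 patients, all completing; P(X>Y) = 0.82; Type I error 0.05; three named measures; all subsets by BIC; leave-one-out refits.

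**Assumptions (not in the protocol).** Normal markers; 3 to 15 responders of 30; and three settings for marker strength and within-group correlation:
- A: AUC 0.82 for each SUV measure and 0.75 for volume; correlation 0.8 between the SUVs and 0.3 with volume.
- B: AUC 0.82 for all three; correlations 0.9 and 0.4.
- C: AUC 0.82 for all three; common correlation 0.5.

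**1. The plan's own figure.** No figure is given for the logistic model. For the rank-sum test, Noether's formula is power = Φ(√(12c(1−c)N)·|p−0.5| − z). With c = 0.5 and N = 30, √90 × 0.32 = 3.04. This gives Φ(3.04 − 1.96) = 85.9% two-sided and Φ(3.04 − 1.645) = 91.8% one-sided. A simulated two-sided test under a normal shift with 15 per group gives about 91%. The stated 90% is therefore attainable, and 0.82 is used here as the marker strength. It equals a shift of √2 × Φ⁻¹(0.82) = √2 × 0.915 = 1.29 SD.

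**2. Why BIC favours a separated model.** Null model: BIC = −2·30·[π ln π + (1−π) ln(1−π)] + ln 30, where π is the responder fraction. This is 45.0, 40.1, 33.4 and 22.9 for 15, 9, 6 and 3 responders. A separated three-marker model has deviance 0, so its BIC is 4 × ln 30 = 4 × 3.40 = 13.6, lower in every case.

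**3. How often separation occurs.** Separation was detected by linear programming in simulated trials. The full-data columns refer to the model with all three markers. A dash means not run.

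| Responders of 30 | A: full data | A: at least one leave-one-out refit | B: full data | B: BIC picks a separated model | C: full data | C: at least one leave-one-out refit |
|---|---|---|---|---|---|---|
| 3 | – | – | 27% | 24% | 30% | 79% |
| 4 | 14% | 50% | – | – | – | – |
| 6 | 6% | 29% | 8.5% | 7.5% | 11% | 38% |
| 9 | – | – | 4.5% | 3.9% | 3% | 17% |
| 10 | 2% | 10% | – | – | – | – |
| 15 | 1% | 6-10% | 1.8% | 1.6% | 2% | 13% |

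Simulation error is about 1-2 points in B and up to 5-6 points elsewhere.

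Two extremes show how much depends on the assumptions. With no true signal and three markers, separation is 0-1%. If only one SUV measure carries signal while the two SUVs correlate 0.9, it is 55-83%. That second case implies a joint shift of about 1.29/√(1−0.81) = 2.97 SD, or an AUC of Φ(2.97/√2) = 0.98, far above the planned effect.

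**4. Coefficient size.** Setting A, after BIC selection, median calibration slope in new patients (1 is ideal):

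| Responders | Maximum likelihood | Firth |
|---|---|---|
| 4 | 0.53 | 0.77 |
| 6 | 0.64 | 0.83 |
| 10 | 0.67 | 0.84 |
| 15 | 0.69 | 0.84 |

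Two further runs gave 0.62-0.70 and 0.54-0.69 for maximum likelihood, against 0.77-0.83 and 0.74-0.84 for Firth. Median log-loss was 0.39-0.56 against 0.34-0.53. Medians are used because log-loss is unbounded under separation, so a mean depends on where the fit stops.

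**5. AUC in new patients.** For 4, 6, 10 and 15 responders: 0.805, 0.808, 0.811 and 0.813 with maximum likelihood; 0.807, 0.811, 0.816 and 0.818 with Firth. The largest gain is 0.005; another run put it at no more than about 0.01 for 10 or 15 responders.

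**6. Scale of a penalised BIC.** Firth's penalty adds ½ ln|I| to the log-likelihood, where I is the information matrix. Multiplying one covariate by s adds ln s for every subset that contains it. For raw fractional changes with an assumed SD of 0.2, the penalised BIC rises by −2 ln 0.2 = 3.22 per covariate relative to SD 1, nearly doubling BIC's own charge of 3.40. In simulation this selected the null model more often and took AUC below maximum likelihood in the same run: 0.71 against 0.77 with 4 responders, and 0.80 against 0.81 with 15. On standardised covariates this did not happen. AUC levels differ between runs, so only contrasts within a run should be read.

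**The case against.** A reader might infer that the fit will usually break down. The documents do not support that. With the three named measures and 6 to 15 responders, separation of the full data is about 1-11%, and at the 15/15 split implied by 7.2 it is 1-2%. Much higher rates follow from assuming about six covariates (19-75% as responders fall from 15 to 3), but no section lists six. Although 7.3 says various measures, the same section names three and limits the model to mid-treatment change, so the list is loosely worded rather than open.

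The count of trials with at least one separated leave-one-out refit also overstates the effect on results, since it is a maximum over 30 refits. With selection repeated in each refit, the average share separated was 13%, 6%, 3% and 0.3% for 4, 6, 10 and 15 responders.

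The strongest objection is that AUC is the performance summary 7.3 specifies, and it hardly moves. The plan does not promise calibration slopes or odds ratios. Separation usually shows in software output, and ridge regression or a cap on model size would also serve. All this stands and limits the severity. It does not remove the point: coefficients are too large even at 15/15, where separation is rare, and a repair chosen after the outcomes are known is worse than one written beforehand.

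**Conclusion.** The point holds in a limited form. As naturally read, 7.3 will tend to produce a selected model with coefficients that are too large (median calibration slope about 0.5-0.7) and has no rule for separation. Separation of the full data is uncommon with the three named measures and 6 to 15 responders (about 1-11%) and more frequent with few responders (about 14% with 4, 27-30% with 3). At least one leave-one-out refit is separated in roughly 6-50% of trials with 4 to 15 responders, and in 79% with 3 under setting C. When separation occurs, BIC usually selects it.

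These sizes rest on normal markers at the strengths stated above (0.82 for the SUV measures, 0.75 or 0.82 for volume) and on responder counts and correlations that the protocol does not give. Severity is low: the model is exploratory, AUC changes little, and the rank tests and correlations behind the primary and secondary objectives are untouched.

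**What to change.** In 7.3:
- State the candidate covariates as the mid-treatment fractional changes in mean SUV, maximum SUV and MRI tumor volume, each standardised.
- Fit every subset, and every leave-one-out refit, with Firth-penalised logistic regression.
- Compute BIC on the standardised scale, or from the ordinary log-likelihood evaluated at the Firth estimates. Do not use penalised-likelihood BIC on raw fractional changes, because the choice of subset would then depend on units.
- Apply an intercept correction before reporting predicted probabilities.

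The cost is SAP wording and standard software, with no new patients, visits or data. Firth pulls predicted probabilities slightly toward 0.5, which the intercept correction repairs. A stated list gives up unplanned covariates. Some overfitting remains (calibration slope about 0.74-0.84), so the model should still be reported as preliminary.

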## **7.0 STATISTICAL CONSIDERATIONS**

### **7.1 Study Design/Study Endpoints**

The purpose of the study is to assess the utility of combined, simultaneous positron emission tomography (PET) and magnetic resonance imaging (MRI), collectively called PET-MR, in assessing response to neoadjuvant radiation therapy in the treatment of high grade sarcomas. The overall design is to image patients with PET-MR at three time points, pre-treatment, mid-treatment, and post-treatment, and correlate quantitative measures from imaging with results of pathology to determine if the mid-treatment PET-MR scan provides information that predicts response to radiation therapy. The primary endpoint is to quantify the association between

pathology determination of response/nonresponse and image metrics from PET at midtreatment. Exploratory aims will address the development of a prediction model for response mid-treatment change in PET and MR, and will evaluate the use of combined PET and MR metrics for prediction compared to each metric alone.

Patients will be identified at the Multidisciplinary Sarcoma Board at UNC. Patients will be high-grade sarcoma patients that are to be treated with neoadjuvant radiation therapy followed by curative intent surgery. Once patient identification occurs, the patient will be assessed for the study via the inclusion and exclusion criteria mentioned above. The patient will then be approached by either the PI, the sarcoma nurse navigator, the radiation oncologist, the surgeon, or a member of their team and the study protocol explained and all risks outlined. If the patient provides informed consent the patient will be enrolled. Demographic data such as patient age, gender, comorbidities, and previous treatments, etc. will be collected. Tumor characteristics such as tumor subtype, grade, Ki-67 score, size, invasion into adjacent organs, etc. will be collected. All data collected will be kept on a password protected, secured server, and all physical documentation will be stored in a locked cabinet. All data will be collected by the PI and co-investigators.

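### Section 7.3 leaves open how the AUC of the BIC-selected model is computed, and the versions it permits can be materially biased with 30 patients

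*Combined protocol and SAP*

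**What the plan says.** Section 7.2 sets the size: "The study will enroll 30 eligible patients that are being treated at UNC Hospitals". For prediction, Section 7.3 says "we will train a logistic regression classifier on the binary response data". The covariates are to be mid-treatment changes in a number of SUV and MRI measures, and the candidates are not listed at that point. The section opens by naming three measures: mean SUV, maximum SUV and MRI tumor volume. The model is chosen as follows: "All subsets selection with BIC will be used to determine the best combination of PET and MRI imaging measures to predict binary response". Performance is to be described by "empirical measures of predictive performance such as leave-one-out cross validation and Receiver-Operating-Characteristic (ROC) curves", the latter summarised by the area under the curve.

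Section 7.1 adds that the exploratory aims "will evaluate the use of combined PET and MR metrics for prediction compared to each metric alone". Section 2.3.1 also lists combined PET-MR prediction as exploratory. The synopsis (Section 1.1) says the results may supply an effect size for planning possible later studies.

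Four things are not stated: the candidate list, whether selection is repeated when a patient is left out, whether the ROC curve uses fitted or held-out predictions, and any optimism correction or interval for the AUC.

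**The concern.** Searching all subsets in 30 patients fits part of the noise. An AUC computed on the patients who chose the model counts that noise as performance. Leaving one patient out after the subset is fixed removes that patient from the coefficients but not from the selection.

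Repeating selection in each fold solves that, but pooling the 30 held-out predictions into one ROC curve brings a different bias. Leaving out a responder lowers the fitted base rate used for that responder, and leaving out a non-responder raises it, so held-out predictions are pushed towards the wrong order.

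At stake are the AUC reported for the exploratory model and the comparison of combined PET and MR with each measure alone. The second is the question that motivates simultaneous imaging.

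**Working it through.** **Nearest figure in the plan.** The documents give no AUC target or precision. Section 7.2 gives about 90% power for the Wilcoxon rank sum test at p = P(X > Y) = 0.82, N = 30, alpha 0.05. That p is the AUC of a single marker, so it serves here as the plan's own signal.
- Noether's formula with equal groups: power = Φ(√(12 × 0.5 × 0.5 × 30) × 0.32 − z) = Φ(3.036 − z). This is 85.9% two-sided (z = 1.960) and 91.8% one-sided (z = 1.645).
- Simulating the two-sided exact test under a normal shift at 15:15 gives 90.9%, so the stated figure is reproduced.

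**Inputs from the documents.** 30 patients; logistic regression; all-subsets BIC; three named measures.

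**Assumptions, because the documents give no figures.** Normal markers; mean and maximum SUV correlated 0.8; signal in mean SUV only (maximum SUV carries it through the correlation, volume carries none); at least one marker kept; 15 of 30 responders, with 8 of 30 as sensitivity. The shift is d = √2 × Φ⁻¹(AUC). For chosen coefficients w, marker mean shifts μ and correlation matrix C, the true AUC is Φ(w′μ / √(2w′Cw)). Each scenario has 300 to 400 runs.

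**Results, three candidates** (mean AUC; LOO = pooled leave-one-out):

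| Responders | Single-marker AUC | Fitted | LOO, selection once | LOO, selection repeated | True |
|---|---|---|---|---|---|
| 15/30 | 0.50 | 0.639 | 0.477 | 0.383 | 0.500 |
| 15/30 | 0.70 | 0.736 | 0.650 | 0.590 | 0.662 |
| 15/30 | 0.82 | 0.840 | 0.789 | 0.757 | 0.800 |
| 8/30 | 0.50 | 0.657 | 0.467 | 0.365 | 0.500 |
| 8/30 | 0.70 | 0.743 | 0.633 | 0.562 | 0.656 |
| 8/30 | 0.82 | 0.843 | 0.775 | 0.730 | 0.793 |

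Bias at 15/30:
- Fitted: 0.639 − 0.500 = +0.139 with no signal; 0.840 − 0.800 = +0.040 at 0.82.
- LOO, selection repeated: 0.383 − 0.500 = −0.117; 0.757 − 0.800 = −0.043.
- LOO, selection once: 0.477 − 0.500 = −0.023; 0.789 − 0.800 = −0.011.

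**Larger pools, selection once, 15/30:**

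| Candidates | Single-marker AUC | Fitted | LOO | True |
|---|---|---|---|---|
| 6 | 0.50 | 0.682 | 0.574 | 0.500 |
| 6 | 0.82 | 0.860 | 0.805 | 0.783 |
| 8 (subsets up to 3) | 0.50 | 0.703 | 0.607 | 0.500 |
| 8 (subsets up to 3) | 0.82 | 0.859 | 0.799 | 0.775 |

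Here both figures are too high.

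**Why pooled leave-one-out runs low.** Take an intercept-only model at 15:15. Each left-out responder is predicted at 14/29 = 0.483 and each left-out non-responder at 15/29 = 0.517, so the pooled AUC is exactly 0 although the model is merely uninformative. If BIC may choose that model, the no-signal means at 15/30 are 0.556 fitted and 0.109 for LOO with selection repeated. Leaving out one patient from each group gives both the same base rate, 14/28, and removes the effect.

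**Combined versus single.** In 300 runs per scenario with signal only in mean SUV, the three-measure model beat mean SUV alone on same-data AUC in 79% to 91% of data sets. At 0.82 and 15:15 the same-data AUCs were 0.841 combined and 0.815 single (+0.026), against true values of 0.783 and 0.817 (−0.034). For the BIC-selected model they were 0.829 and 0.815 (+0.014), against 0.797 and 0.817 (−0.020).

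**Alternatives, selection repeated in every resample** (three candidates, 15/30; 75 random pairs and 40 bootstrap samples per data set):

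| Single-marker AUC | Fitted | Bootstrap-corrected | Leave-pair-out | True |
|---|---|---|---|---|
| 0.50 | 0.637 | 0.540 | 0.500 | 0.500 |
| 0.70 | 0.722 | 0.652 | 0.657 | 0.655 |
| 0.82 | 0.826 | 0.784 | 0.790 | 0.801 |

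**The case against.** The strongest reply is that the plan already includes internal validation. Section 7.3 names "leave-one-out cross validation and Receiver-Operating-Characteristic (ROC) curves" together, and a ROC curve drawn from held-out predictions is as natural a reading as one from fitted values. A reader might infer that the plan commits to a same-data ROC area; the text does not say so. This stands, and the point is therefore about an open procedure. It does not remove the problem, because pooled leave-one-out with selection repeated is biased too.

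Three further inferences go too far:
- **That the two measures always err in opposite directions.** They do with three candidates, on average, but not with six or eight when selection is done once.
- **That the planned figures cannot tell a useless model from a useful one.** On average they can: 0.639 against 0.840 fitted, and 0.383 against 0.757 for leave-one-out with selection repeated. With selection done once at 15:15, a leave-one-out AUC of 0.70 or more appeared in 6% of no-signal data sets and in 78% at p = 0.82.
- **That the combination wins automatically on the data that chose it.** BIC picked a single measure in about 95% of no-signal data sets with three candidates. The reversal shown above is an average in particular scenarios.

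Two more replies stand. The aim is exploratory, and the effect size defined in Section 7.2 is the single-marker P(X > Y), which subset selection does not touch. Sampling error also exceeds the bias at p = 0.82: the run-to-run SD was 0.074 for the fitted AUC and 0.103 for leave-one-out with selection repeated, or about ±0.15 and ±0.20 at 1.96 SD. That is a reason to require an interval.

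**Conclusion.** The point holds as a specification gap with measurable consequences. Section 7.3 permits several AUCs for the same model, and with three candidates and no signal their averages run from 0.38 to 0.64 around a truth of 0.50. Near the plan's own signal the error is modest: about +0.04 fitted and −0.01 to −0.04 for leave-one-out. It would therefore be too strong to say that the reported AUC will be wrong; it can be materially biased, most of all when the markers carry little information or the candidate pool is large.

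The effect is confined to the exploratory prediction aim and the combined-versus-single comparison. The primary Wilcoxon comparison and the secondary objectives do not depend on it.

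The sizes rest on the assumed marker distributions, correlation, signal structure and responder share, and on keeping at least one marker. Leave-one-out reported as an error rate, instead of a pooled AUC, was not assessed.

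**What to change.** Amend Section 7.3 to:
- limit the candidates to the pre- to mid-treatment changes in the three measures it names (mean SUV, maximum SUV, MRI tumor volume), and say whether a model with no measures may be chosen;
- repeat the all-subsets BIC selection and the refit in every resample;
- report a leave-pair-out AUC, with ties scored one half, for the combined model and for each single measure, each with a confidence interval whose method is named in advance. A bootstrap optimism-corrected AUC with selection repeated is an acceptable alternative; it was somewhat high with no signal (0.540 against 0.500) and similar otherwise;
- state which predictions feed any ROC curve, and label a same-data ROC area as descriptive.

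The cost is a few sentences and a little computing: at most 15 × 15 = 225 pairs times 2³ − 1 = 7 non-empty subsets, or 1,575 small logistic fits for the combined model's estimate, before the interval. No new data are needed. The downside is that reported AUCs will generally be lower than the same-data ones, and the intervals will be wide.
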